Full study Title:	Morbidity, Mortality And Risk Factors of Mpox in HIV negative high-risk Sexual health clinic attenders and People Living With HIV - MASH Study	
Short title/Acronym	MASH	
Clinical Phase	Observational Retrospective Cohort Study	
Study Design	Case-descriptive study	
Study Population	PLWHIV (people living with HIV) who are currently sexually active and HIV negative high-risk Sexual Health Clinic attenders (PrEP users) with Mpox	
End of study data collection	Date of clinical resolution e.g. lesion resolution, hospital discharge or death (up to 3 months)	
Planned Sample Size	Approximately 2000	
Eligibility Criteria	at least 18 years of age with either documented HIV-1 infection or PrEP clinic attenders, and confirmed MPX infection by documented result on PCR testing on skin and/or mucosal and/or any anatomical site.	
Indications	HIV & MPX; PrEP patients & MPX	
Methodology	Only real-world, routinely collected, retrospective data will be used for this study collected from patients who during the study period have had confirmed Mpox. Pseudonymised data will be transcribed into the eCRF (electronic Case Report Form) system from source data at each clinical site or from existing databases, where appropriate. No personal identifiable data will be transmitted to NEAT ID.	
Number of sites	Up to 12 sites in up to 7 countries	
Objectives	
Primary
 
 1. To describe and compare outcomes of MPX in PLWHIV and an HIV-negative population of people using pre-exposure HIV prophylaxis (PrEP users) 2. To identify risk factors for specific MPX outcomes (including CD4 cell count nadir and current CD4 count in PLWHIV) 	
Secondary
 
 1. To estimate the approximate prevalence of MPX in PLWHIV and PrEP users in this retrospective cohort 2. To describe clinical manifestation of MPX and response to MPX treatment in PLWHIV and PrEP users 3. To describe the co-morbidities in PLWHIV and PrEP users

Outcome Measures	Primary	Secondary
	
 1. Severity of lesions, clinical complications, percentage of hospitalisations, death. 2. Differences in the clinical manifestation of MPX in PLWHIV and PrEP users 3. Differences in the clinical manifestation of MPX in PLWHIV by CD4 and VL 	
 • Number of MPX patients attending as a percentage of total number of patients the sites have seen over a set period of time (first Mpox patient to last Mpox patient at site) • time to lesion resolution (if known) • Length of stay in hospital • Differences in the clinical manifestation of MPX in PLWHIV and PrEP users by comorbidities.

LIST OF ABBREVIATIONS

Acronym	Description
ACCI	Age-adjusted Charlson Comorbidity Index
ART	Antiretroviral Therapy/Treatment
ARV	Antiretroviral
CCI	Charlson Comorbidity Index
CI	Chief Investigator
CRF	Case Report Form
CRO	Contract Research Organisation
CTA	Clinical Trial Authorisation
EC	European Commission
ECMO	Extracorporeal Membrane Oxygenation
eCRF	Electronic Case Report Form
EMEA	European Medicines Agency
EU	European Union
EUCTD	European Clinical Trials Directive
GDPR	General Data Protection Regulation
GDocP	Good Documentation Practice
GPP	Good Pharmacoepidemiology Practice
HIV	Human Immunodeficiency Virus
ICH	International Conference on Harmonisation of technical requirements for registration of pharmaceuticals for human use.
ISF	Investigator Site File
ISPE	International Society for Pharmacoepidemiology
MS	Member State
MPX	MPox (previously known as Monkeypox)
MSM	Men who have sexual activity with men
PI	Principal Investigator
PLWHIV	People living with HIV
PrEP	Pre-exposure prophylaxis
PrEPHRA	HIV negative, high risk sexual health clinic attenders
R&D	Research & Development
REC	Research Ethics Committee
SOP	Standard Operating Procedure
TMF	Trial Master File
VFD(s)	Ventilator-Free Day(s)
WHO	World Health Organisation

1 BACKGROUND

Mpox (or MPX) (previously known as Monkeypox) is an acute febrile rash illness caused by the mpox virus, an orthopox virus related to variola virus (causative agent of smallpox), cowpox virus and the vaccine strain vaccinia virus.

Since the first identification of a mpox infection in humans in 1970, the majority of human cases have been reported from Africa, including sporadic outbreaks that usually resulted from contact with wildlife reservoirs, in particular rodents. Animal-to-human (zoonotic) transmission can result from direct contact with the blood, bodily fluids, or cutaneous or mucosal lesions of infected animals. There are two distinct genetic clades of the mpox virus: the central African or Congo Basin clade (Clade 1) and the west African clade (Clade 2). The case fatality ratio of mpox has historically ranged from 0 to 11 % in the general population and has been higher among young children. In recent times, the case fatality ratio has been around 3–6%. The central African (Congo Basin) clade has historically caused more disease and was thought to be more transmissible. (WHO fact sheet) Human-to-human transmission can result from close contact with respiratory secretions, skin lesions of an infected person or recently contaminated objects. Transmission via droplet respiratory particles usually requires prolonged face-to-face contact. (WHO fact sheet) Cross-immunity exists between different orthopox viruses, and, in the past, vaccination against smallpox was protective against mpox infection. However, the global smallpox vaccination campaigns were discontinued after eradication of the disease, likely leaving the population below 40 to 50 years of age (depending on the country) more susceptible to mpox.

Mpox is usually a self-limited disease with the symptoms lasting from 2 to 4 weeks. Severe cases occur more commonly among children and are related to the extent of virus exposure, patient health status and nature of complications. Underlying immune deficiencies may lead to worse outcomes. Complications of mpox can include secondary infections, bronchopneumonia, sepsis, encephalitis, and infection of the cornea with ensuing loss of vision.

Until recently, there have been very few travel-associated cases in non-African countries, with very limited onward transmission. However, following notification from the United Kingdom to WHO on the 15th of May 2022, of two confirmed and one probable case of mpox, person-to-person transmission of mpox has been increasingly observed in countries outside of Africa. By August 5th, 2022, 28,220 cases of mpox infection have been reported in 88 locations worldwide, 27,875 of whom in countries that have not historically reported mpox. The largest numbers of cases have been reported in Europe. (Joint ECDC-WHO Regional Office for Europe Mpox Surveillance Bulletin (europa.eu)) The viruses associated with these cases are most closely related to clade 2 but have some genetic differences and has been tentatively named Clade 3.

An early report indicates that patients in the epidemic outside Africa may present with a clinical picture that differs from the usual presentation. 95% of patients had a rash, 73% had anogenital lesions and 41% had mucosal lesions. 13% of the patients were hospitalized. Reasons for hospitalization included pain management (mostly severe anorectal pain), soft-tissue superinfection, pharyngitis limiting oral intake, eye lesions, acute kidney injury, myocarditis and/or infection-control purposes. In this report, 98% were Men who have sexual activity with men (MSM) and 41% had Human Immunodeficiency Virus (HIV) infection – these groups are currently considered at a higher epidemiological risk to contract the infection. (Thornhill e.a. NEJM 2022)

A vaccine campaign with vaccinia virus (smallpox vaccine) has been started for specific risk groups; this may impact the transmission of mpox virus, but clinical evidence is still lacking and available dosages are limited. Furthermore, it is feared that the epidemic may extend outside of the currently defined risk groups.

Currently, antiviral medication for mpox that has been properly evaluated in clinical trials is not available, but several antivirals have demonstrated activity in vitro and in animal models. The most promising is tecovirimat, an oral anti-viral drug that inhibits the cytopathic effect of mpox virus on cell cultures and reduces plaque formation. (Smith, AAC 2009) Furthermore, tecovirimat has been found to protect non-human primates, when administered at three days post challenge with lethal doses of mpox virus. (Jordan *et al.* AAC 2009).

2 RATIONALE

We have few data to suggest whether or not People Living with HIV (PLWHIV) are at an increased risk of serious illness or death or there is an impact of being HIV positive on outcomes or clinical presentation or if there is any dependence on CD4 cell count and viral load.

The most affected countries in Europe include Spain, the United Kingdom, Germany, France and the Netherlands. The majority of the cases identified to date have been among men who have sexual activity with men (MSM). There has been a preponderance of genital, perianal and mucosal lesions, rather than the centrifugal rash classically described for mpox. An early report indicates that 95% of patients had a rash, 73% had anogenital lesions and 41% had mucosal lesions. Some of the lesions persist for a long period and some patients have required hospitalisation for pain management or treatment of secondary skin infections. 13% of the patients were hospitalized. Reasons for hospitalization included pain management (mostly severe anorectal pain), soft-tissue superinfection, pharyngitis limiting oral intake, eye lesions, acute kidney injury, myocarditis and/or infection-control purposes. In this report, 98% were MSM and 41% had HIV infection. (Thornhill *et al.* NEJM 2022)

Rapid data collection and analysis about MPX in PLWHIV will depend on international multi-centre collaborations, for which NEAT ID has a strong expertise. The majority of PLWHIV in Europe are in routine clinical care, allowing for a comprehensive data collection about MPX and studying the impact of HIV drugs and specific risk factors. The NEAT ID MPX Coinfection Dashboard was established in August 2022 to collect data on the number of PLWHIV co-infected with MPX and anonymised, aggregated data from this dashboard on 249 PLWHIV who attended Chelsea and Westminster Hospital between May 15th and December 15th 2022 were recently presented at the CROI 2023 conference ([name] *et al*, CROI 2023). It has provided evidence that a significant number of PLWHIV were suffering from MPX in Europe at that time and that these individuals can be enrolled into an Epidemiology and Real-World- Data study.

A feasibility study of HIV negative patients receiving Pre-exposure prophylaxis (PrEP) across the NEAT ID network has identified 45 sites that provide PrEP services for a total of 27,416 PrEP users with 1,361 new PrEP initiators each month.

There are two central questions to address:

1. Do PLWHIV have a more severe disease course and outcomes from MPX as compared to MPX in PrEP user?
2. Are there particular factors, (e.g. CD4 T-cell nadir, current CD4 T-cell count, co-morbidities) within the group of PLWHIV, which put them at risk for a more severe MPX disease course?

3 OBJECTIVES AND OUTCOME MEASURES/ENDPOINTS

It is hypothesised that HIV infection could be a risk factor for more severe MPX outcomes and that advanced immunodeficiency as defined by current CD4 T-cell count or CD4 T-cell nadir is a risk factor for more severe MPX outcomes in PLWHIV.

3.1 Primary objective

1. To describe and compare outcomes of MPX in People Living with HIV (PLWHIV) and a HIV-negative population of people using pre-exposure HIV prophylaxis (PrEP users)
2. To identify risk factors for specific MPX outcomes (including CD4 cell count nadir and current CD4 count in PLWHIV)

3.2 Secondary objectives

1. To estimate the approximate prevalence of MPX in PLWHIV and PrEP users in this retrospective cohort
2. To describe clinical manifestation of MPX and response to MPX treatment in PLWHIV and PrEP users
3. To describe the co-morbidities in PLWHIV and PrEP users

3.3 Primary endpoint/outcome

- Severity of lesions, clinical complications, percentage of hospitalizations*, death.
- Differences in the clinical manifestation of MPX in PLWHIV and PrEP users
- Differences in the clinical manifestation of MPX in PLWHIV by CD4 and VL.

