7.2 Statistical analysis plan

This is primarily a descriptive retrospective data cohort study but will compare MPX severity between 1) PLWHIV and PrEP users, to show whether HIV infection is associated with more severe MPX; 2) PLWHIV with different characteristics, to identify factors associated with severe MPX within HIV infected population.

All enrolled participants who meet the eligibility criteria will be included in the analysis population (full analysis population). All primary and secondary endpoints will be performed with the full analysis population.

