The second primary outcome analysis will be performed between PLWHIV with MPX versus PrEP users with MPX. The endpoint is to assess differences in clinical manifestations of MPX between the groups. Unadjusted and adjusted odds ratios (ORs) will be calculated using the logistic regression models to compare the rates of clinical manifestations between PLWHIH and PrEP users. The adjusted variables will be the following (potential confounders): Age (<30 vs 30-40 vs >40 years); Sex at birth (female vs male); Comorbidities; multiple sexual partners (yes vs no); number of sexual partners in the last 3 months prior to MPX diagnosis; and smallpox vaccination history (yes vs no).

The third primary outcome analysis will be performed within the PLWHIV group. The endpoint is to evaluate the characteristics of HIV infection associated with severe mpox. Univariable and multivariable logistic regression models will be used to assess factors associated with severe mpox in PLWHIV. The following variables will be evaluated: time since HIV diagnosis (years); current ART; CDC disease stage; CD4 cell nadir; last CD4 cell count/HIV-RNA before MPX diagnosis (including CD4% and CD4/CD8 ratio). Variables achieving $P < 0.20$ in the univariable analysis will be retained for the multivariable analysis.

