7.5 Secondary outcome analysis

All secondary outcome analysis will be performed on PLWHIV with MPX compared to PrEP users with MPX.

The prevalence of MPX per site during the study period will be estimated by the number of MPX patients attending the site divided by the total number of patients the sites saw during the study period. The 95%

Confidence Interval of the prevalence will be calculated with the exact Clopper-Pearson method. Fisher exact test will be used to compare the prevalence of MPX in HIV-infected individuals to that of PrEP users.

The length of stay in hospital will be estimated using competing risk models with death as a competing event. Gray's test will be used to compare the duration of hospitalisation between PLWHIV and PrEP users. Unadjusted and adjusted sub-distribution hazard ratios (sHR) will be calculated using competing risk models with death as a competing event. The duration of hospitalization will be defined by the time (days) from hospitalization to hospital discharge or last observation. Adjustment variables will include: Age (<30 vs 30-40 vs >40 years); Sex at birth (female vs male); Comorbidities; multiple sexual partners (yes vs no); number of sexual partners in the last 3 months prior to mpox diagnosis; and Orthopoxvirus vaccination history (yes vs no).

Subgroup analyses for clinical manifestation in MPX will be conducted to assess the difference between PLWHIV and PrEP users across comorbidities. The following comorbidities will be assessed: diabetes mellitus, immunosuppression (e.g. solid organ transplant), chronic kidney or liver disease, mental health illness. Adjusted odds ratio will be calculated to compare PLWHIV and PrEP users within subgroup using logistic regression models. Adjustment variables will include: Age (<30 vs 30-40 vs >40 years); Sex at birth (female vs male); multiple sexual partners (yes vs no); number of sexual partners in the last 3 months prior to mpox diagnosis; and smallpox vaccination history (yes vs no).

Heterogeneity in the impact of HIV infection on clinical manifestations based on comorbidities will be assessed by including terms for interactions between patient status (PLWH and PrEP users) and the comorbidity variable in multivariable logistic regression models. All variables described above for adjustments will be included in the multivariable models.

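### The third primary endpoint (manifestations in people with HIV by CD4 and viral load) has no matching analysis, because the third primary analysis uses severe mpox as its outcome

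*Combined protocol and SAP*

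**What the plan says.** The synopsis and section 3.3 give three primary endpoint bullets. The third is "Differences in the clinical manifestation of MPX in PLWHIV by CD4 and VL". Its outcome is clinical manifestation, its exposures are CD4 and viral load, and its population is people living with HIV.

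Section 7.4 describes the third primary analysis differently: "The endpoint is to evaluate the characteristics of HIV infection associated with severe mpox". The method follows: "Univariable and multivariable logistic regression models will be used to assess factors associated with severe mpox in PLWHIV". The candidate variables are years since HIV diagnosis, current antiretroviral therapy, CDC stage, CD4 nadir, and last CD4 and HIV-RNA before the mpox diagnosis. Those reaching P < 0.20 "in the univariable analysis will be retained for the multivariable analysis".

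Section 7.2 describes the same within-group comparison as one of "PLWHIV with different characteristics, to identify factors associated with severe MPX within HIV infected population". For the secondary analyses, 7.5 states: "All secondary outcome analysis will be performed on PLWHIV with MPX compared to PrEP users with MPX".

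**The concern.** A reader who starts from the endpoint list expects a result showing whether the presentation of mpox (lesion sites and symptoms, for example) differs by immune status and viral control among people with HIV. A reader who starts from 7.4 finds a risk-factor model for a single severe or not-severe outcome. These are different results, and the second does not contain the first.

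If the plan is followed literally, a listed primary endpoint goes unreported. If the analysis is built later, the manifestations, the coding of CD4 and viral load, and the adjustment set would all be chosen with the data in hand. The rationale in section 2 names the possible dependence of outcomes or presentation on CD4 and viral load among the evidence gaps behind the study, so the bullet is unlikely to be a stray line.

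**Working it through.** The plan gives no power or sample-size calculation for this endpoint, so there is no figure to reproduce. The check is to match the endpoint with every planned analysis on outcome, population and exposure.

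| Analysis | Outcome | Population and contrast | CD4 or viral load as exposure | Delivers the third endpoint? |
|---|---|---|---|---|
| Endpoint bullet 3 (3.3, synopsis) | Manifestations | Within people with HIV | Yes | (target) |
| First primary (7.4) | Lesion severity, lesion resolution time, hospitalisation, death | HIV vs PrEP users | No | No |
| Second primary (7.4) | Manifestations | HIV vs PrEP users | No | No: right outcome, other contrast |
| Third primary (7.4) | Severe mpox | Within people with HIV | Yes, as screened candidates | No: right population and exposures, other outcome |
| Secondary (7.5) | Prevalence, length of stay, manifestations by comorbidity | HIV vs PrEP users | No | No |

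The two nearest analyses each miss one element. The second uses its logistic models "to compare the rates of clinical manifestations between" the HIV and PrEP groups, so it has the outcome but not the exposure. The third has the exposures but not the outcome. Section 7.5 cannot fill the gap, because its opening sentence confines every secondary analysis to the between-group contrast.

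The screen adds a second, smaller problem. Univariable estimates for CD4 and HIV-RNA are produced whatever their P values. The multivariable model takes only variables with P < 0.20, so an adjusted estimate for either exposure named in the endpoint may not exist. The candidate list for this model also contains only HIV-related variables. The age, sex, comorbidity, partner and vaccination adjustments are stated for the first and second analyses.

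The data needed are already planned. Section 6.2 collects last CD4, last HIV-RNA, signs and symptoms, six lesion sites and nine complications.

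**The case against.** The best defence is that 6.2 files reported signs and symptoms under a severity label, so severe mpox might be meant to cover manifestations. This does not hold. Section 3.3 lists lesion severity and manifestations in separate bullets, and 7.4 analyses them separately. A single yes/no outcome cannot show which manifestations vary with CD4 or viral load, and 7.4 gives no rule for deriving severe mpox from signs and symptoms.

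A second defence has more force. The second central question in section 2, the hypothesis in section 3, primary objective 2 and section 7.2 all frame the within-HIV question as one of severity or outcomes. Describing manifestations is a secondary objective in 3.2. On that reading the third analysis is what the study wants, and the bullet in 3.3 is the outlier. That stands as a reason to keep the severe-mpox model and to offer rewording as an alternative. It does not remove the conflict, because the bullet is still listed as primary in two places.

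A third defence is that the study is mainly descriptive. Section 7.2 says it will also compare groups, and for this endpoint the plan specifies neither a model nor a tabulation by CD4 or viral load.

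Two stronger readings are tempting, and the documents support neither.

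- A reader might infer that the immune-status question goes unanswered. It does not: CD4 and HIV-RNA are examined against severe mpox, and their univariable estimates are always produced.
- A reader might infer that a rare outcome has replaced a common one, with a loss of precision. Section 7.4 does not define severe mpox, so its frequency is unknown. Hospitalisation is an uncertain stand-in: 53/907 = 5.8% on the network dashboard (6.1), but 13% in the early report cited in sections 1 and 2. The UK definition in 6.2 has several criteria beyond hospitalisation.

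**Conclusion.** The point holds as a conflict between a stated primary endpoint and its stated analysis. One of three primary endpoint bullets has no analysis with the right outcome, although population and exposures are right in the third primary analysis. Adjusted estimates for CD4 and HIV-RNA are also not guaranteed in that analysis. The conclusion rests on the text of 3.3, the synopsis, 7.2, 7.4 and 7.5. It needs no assumption about event rates or about the split between the two groups, which the plan does not fix. No claim is made about lost precision or the relative rarity of the outcomes. The matter should be settled before analysis, and it is cheap to settle.

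**What to change.** In 7.4, add an analysis within people with HIV. Fit logistic models of the same manifestations used in the second primary analysis, with last CD4 and last HIV-RNA as exposures. Keep both in the model regardless of the P < 0.20 screen, and adjust for the confounders already listed in 7.4. State in advance which manifestations are included and how CD4 and HIV-RNA are coded. Keep the severe-mpox model and label it as the analysis of primary objective 2.

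The cost is SAP wording and more models on data already being collected, with more comparisons. Section 7.4 does not list its manifestations. As an illustration, if each exposure enters as one term, the six lesion sites alone give 6 × 2 = 12 adjusted odds ratios. Adding the nine complications gives 15 × 2 = 30. These should be reported as estimates with confidence intervals and not read as a set of significance tests.

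If the sponsor did not intend this endpoint, the alternative is to reword it as severe mpox in both 3.3 and the synopsis and to define that outcome for the analysis. The UK definition in 6.2 would need care here. It counts confirmed infection in immunocompromised people as severe whatever the clinical course, which would make an association with CD4 partly circular.
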